8.1. Primary Efficacy Endpoint and Analysis

The primary efficacy endpoint is defined as the proportion of patients who have converted from AF within 90 min from the start of infusion, and subsequently have no AF recurrence within 1 min of conversion from AF.

For the analysis of the primary endpoint (proportion of patients who have cardioversion within 90 min from the start of infusion) a Bayesian model will be utilised. The prior probability of success at a dose, d , is modelled with a $P_d \sim \text{Beta}(1,1)$ prior (uniform) for each dose. Across both Parts 1 and 2 of the study, the potential doses (arms) in the trial are $d = 0$ (placebo), 2, 3, 4, 5, and 6 (all mg/kg dose units).

Let X_d be the number of successes and N_d be the number of observations at dose d . The posterior distribution is calculated for each dose independently using a Beta posterior distribution,

$$P_d \sim \text{Beta}(1 + X_d, 1 + N_d - X_d).$$

The adaptive design utilises the probability that the response rate at a dose is greater than a 65% success rate. This is ($P_d > 0.65$), for each dose d .

This modelling will occur for each interim analysis, and at the final analysis as primary method. At the conclusion of the study, each AP30663 dose will be considered to be superior to placebo, if the posterior probability of AP30663 dose having a higher success rate than placebo is greater than 0.95.

Further to the above, the primary endpoint will also be analysed by means of a logistic regression model. The model will include treatment and duration of current AF episode.

Duration of current AF episode (in hours) = date/time of randomisation – date/time of AF symptom onset

If no time of AF symptom onset is available, '00:00' will be used for the calculation of the duration.

All statistical tests will be 2-sided and conducted at the 5% significance level. All presented confidence intervals will be 2-sided 95% confidence intervals.

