3.7. Treatment Assignment & Blinding

For Part 1 of the study, eligible patients will be randomised 1:1 (approximately 36 patients randomised to AP30663 or placebo). An additional 18 to 72 patients will be randomised cumulatively in a 2:1 ratio to 1 or more doses of AP30663 (dependent on dose arms open at time of randomisation) or placebo in Part 2 using an interactive web randomisation system (IWRS).

Two separate lists will be utilised for the study, one for Part 1 and a separate one for Part 2. Both lists will be provided by a separate unblinded biostatistical team and provided to the IWRS.

Acesion Pharma, investigators, and patients will remain blinded to the study treatment allocation until the end of the study. The randomisation list will be kept secure from the study team, investigators, and patients throughout the conduct of the study and until unblinding is authorised by Acesion Pharma and the blinded lead study statistician. The DMC will be unblinded according to the DMC charter, and a separate unblinded statistical team will be assigned to provide the analyses to the DMC and Interim Analysis. Further details of blinded and unblinded personnel will be included in the DMC charter.

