6.6. Subgroups

No subgroup for this study.

This document is confidential.

7. Demographic, Other Baseline Characteristics and Medication

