7.2. Demographic and Other Baseline Characteristics

Gender and child-bearing potential (female patients only), ethnicity will be summarized by the number and percentage of patients in each treatment group. Age (years) will be summarized using descriptive summary statistics.

Demographics parameters will be also presented by cohort at each Interim Analysis.

Data from transthoracic echo (TTE) will be presented using summary statistics. Height and baseline weight will be also summarized.

Duration of current AF episode (in hours) (derivation see section 8.1) and time since initial AF diagnosis (in years) will be summarized in addition.

Time since initial AF diagnosis (in years) = date of randomization – date of initial AF diagnosis (based on MHDECOD = 'Atrial Fibrillation')

In case of an incomplete date of initial AF diagnosis, the first day of the month will be used for a missing day, 1st January will be used for a missing day and month.

All demographic data will be presented in a data listing.

This document is confidential.

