8.2.2. Proportion of patients with relapse of AF within 5 min (IRAF)

The proportion of patients with relapse of AF within 5 min (IRAF) following pharmacological or DC cardioversion will be presented by treatment and analysed using a logistic regression model. The model will include treatment, and duration of current AF episode.

In addition the same analysis will be done for the proportion of patients with relapse of AF within 5 min (IRAF) following pharmacological cardioversion only.

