 - If Dose d was the largest dose thus far open, and Dose d is < 6 mg/kg, then dose d + 1 will be opened.

The study will continue until all doses of AP30663 have been closed or the maximum of 72 patients during Part 2 (up to 108 patients total across Part 1 and Part 2) have been enrolled.

While the algorithm, and the DMC's decision for dose increase/decrease, is based on AF conversion rate only, the DMC will also convene to review safety and tolerability data at defined time points; review of this data may also lead to further decisions being made by the DMC.

This document is confidential.

12. Changes from Analysis Planned in Protocol

None

This document is confidential.

13. Reference List

None

This document is confidential.

14. Programming Considerations

All tables, figures, listings (TFLs), and statistical analyses will be generated using SAS for Windows, Release 9.4. (SAS Institute Inc., Cary, NC, USA). Computer-generated table, listing and figure output will adhere to the following specifications.

The static analysis based on plasma concentration will be performed using a non-compartmental analysis (NCA), the PK analyses will be performed by Syneos Health using Phoenix WinNonlin® (release 8.0 or higher) and all other analyses and summaries will be produced using Statistical Analysis System (SAS®) version 9.4 (or higher).

PK analyses will be performed using NONMEM® version 7.4.

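### The final rule pools placebo over two separately randomised Parts with no planned same-Part check, and the Appendix I sample contrasts do not compare each dose with placebo

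*SAP*

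**What the plan says.** **Final rule and placebo arm.** SAP 8.1 gives each arm a Beta(1,1) prior and calls a dose superior if its posterior probability of beating placebo exceeds 0.95. Placebo is a single arm, d = 0: "Across both Parts 1 and 2 of the study, the potential doses (arms) in the trial are" placebo and 2 to 6 mg/kg. On use of the model: "This modelling will occur for each interim analysis, and at the final analysis as primary method". The examples in Protocol 17.3 accumulate placebo to 42 patients and use that one arm for every dose.

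**Two Parts.** SAP 3.7: "Two separate lists will be utilised for the study, one for Part 1 and a separate one for Part 2". Allocation is 1:1 in Part 1 and 2:1 in Part 2. Under SAP 11, 3 mg/kg is stopped after Part 1 whatever its result, and the other doses open only in Part 2. On duration: "The study will continue until all doses of AP30663 have been closed or the maximum of 72 patients during Part 2" are enrolled.

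**By-Part analysis.** SAP 6.6: "No subgroup for this study". On the logistic regression, SAP 8.1 says "The model will include treatment and duration of current AF episode", and SAP 8.2.3 uses the same two terms. SAP 7.2 says "Demographics parameters will be also presented by cohort at each Interim Analysis", and disposition is also tabulated by cohort, but conversion is not.

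**Sample code.** SAP Appendix I offers one logistic program for all proportion endpoints. The treatment variable is `trtp`, reference-coded with Placebo as reference. The two contrasts are `trt 1 -1 0` and `trt 1 0 -1`, and their estimates are saved to a dataset.

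**The concern.** Each dose is compared with some placebo patients who were not randomised alongside it. At 108 patients, 24 of the 42 controls for 3 mg/kg come from the other Part, as do 18 of the 42 for every other dose. If background conversion differed between the Parts, the difference would enter the superiority call directly: a rise favours Part 2 doses, and a fall favours 3 mg/kg. The study is meant to identify a dose for later-phase work, and no planned output tests this. A by-Part check chosen after unblinding would carry less weight than one written down now.

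The sample code is a separate matter. A programmer who fixed only the variable name would obtain contrasts that run but answer a different question.

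**Working it through.** **1. The plan's own figures.** With Beta(1,1) priors, Pr(P_d > P_0) = ∫ f(p; 1+X_d, 1+N_d−X_d) · F(p; 1+X_0, 1+N_0−X_0) dp, where f is the Beta density and F the Beta distribution function. For Example 2 Dose 5 (5/12 against 8/42) this gives 0.946, but the protocol prints 0.959. Three other final posteriors also fail to reproduce: Example 2 Dose 3 is 0.645 (printed 0.690), Example 3 Dose 3 is 0.991 (printed 0.994), and Example 4 Dose 2 is 0.935 (printed 0.947). Recomputed values are therefore used on both sides below.

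**2. Pooled against same-Part placebo in the examples.** Part 2 placebo is the final count minus the Part 1 count: 6−2 = 4/24, 8−2 = 6/24, 8−2 = 6/24 and 6−3 = 3/24 in Examples 1 to 4.

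| Example | Dose | Pooled | Same-Part |
|---|---|---|---|
| 1 | 3 | 0.999 | 0.997 |
| 1 | 4 | 1.000 | 0.998 |
| 1 | 5 | 1.000 | 1.000 |
| 2 | 3 | 0.645 | 0.798 |
| 2 | 5 | 0.946 | 0.847 |
| 2 | 6 | 1.000 | 0.999 |
| 3 | 3 | 0.991 | 0.994 |
| 3 | 4 | 1.000 | 0.998 |
| 3 | 5 | 1.000 | 1.000 |
| 4 | 2 | 0.935 | 0.928 |
| 4 | 3 | 1.000 | 1.000 |
| 4 | 5 | 1.000 | 1.000 |

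None of the 12 changes side of 0.95.

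**3. Effect of an assumed drift.** The documents give no drift, so these rates are assumptions. Pooled placebo is 18 + 12 = 30 if the study stops at 72 patients and 18 + 24 = 42 at 108. Exact binomial enumeration of the 0.95 rule at fixed sizes, with an ineffective dose, gives:
- Placebo rises from 10% to 20%, 12-patient Part 2 dose: 12.7% (30 controls) or 12.0% (42) pooled, against 5.1% (12) or 5.2% (24) same-Part.
- Placebo falls from 20% to 10%, 18 patients on 3 mg/kg: 8.6% (30) or 14.4% (42) pooled, against 4.6% (18) same-Part.

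**4. The same rise within the adaptive design.** A simulation with the SAP 11 opening and closing rules gives 11.9% pooled against 4.4% same-Part for Dose 5. The study stops at 72 patients in 96% of trials. With 12 patients, a dose closes for low response at 5 or fewer conversions, because Pr(P_d > 0.65) is 0.046 at 5/12 and 0.129 at 6/12. In a 40,000-trial run, every false Dose 5 call fell on a dose already closed by this rule. A false call on a Part 2 dose not so closed occurred in about 0.03% of trials. With no drift (placebo 10–20%), the per-dose rate is 4.2–4.9% pooled and 2.4–4.6% same-Part.

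**5. A Part term in the logistic model.** Each dose sits in one Part, so only placebo informs the Part effect. On Example 1, without AF duration:
- Pooled odds ratios: (10/8)/(6/36) = 7.5, (8/4)/(6/36) = 12.0, (28/8)/(6/36) = 21.0.
- With Part: (10/8)/(2/16) = 10.0, (8/4)/(4/20) = 10.0, (28/8)/(4/20) = 17.5. These are the same-Part odds ratios.
- Standard error of the 3 mg/kg log odds ratio: √(1/10+1/8+1/6+1/36) = 0.65 pooled, √(1/10+1/8+1/2+1/16) = 0.89 with Part.

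**6. The sample contrasts.** Under reference coding, three coefficients stand for three active doses. `1 -1 0` is then first against second dose, and `1 0 -1` is first against third. On Example 1, if the variable name were corrected, they would return (10/8)/(8/4) = 0.625 and (10/8)/(28/8) = 0.357. The odds ratios against placebo are 7.5, 12.0 and 21.0. As printed, the contrasts refer to `trt`, which is in neither the CLASS nor the MODEL statement.

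**The case against.** Pooling is deliberate and disclosed, and eligibility, endpoint and schedule are the same in both Parts. This is a Phase 2a proof of concept, and a larger control arm is worth having. The logistic model adjusts for AF duration, so drift from that source is partly handled on the supportive side. Placebo conversion by Part can be worked out from successive interim outputs, because Table 14.2.1.1.1 is delivered at each interim analysis. All of this stands. It limits the point to a missing robustness check.

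Two stronger readings are tempting. First, a reader might set the printed 0.959 for Example 2 Dose 5 beside the same-Part 0.847 and infer that pooling creates the superiority call. It does not: 0.959 does not reproduce from the stated prior and counts, and the recomputed pooled value, 0.946, already fails. That discrepancy is a separate error. Second, the simulated chance of a false call on any dose under the assumed rise (21.4% pooled, 9.7% same-Part) might be read as the design's error rate. It needs a doubling of background conversion and no working dose, and nearly all the false Part 2 calls fall on doses already closed. Under the reverse drift there is no net increase (10.2% against 10.5%).

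On the code, it is labelled an example, and the contrasts as printed would need correcting before they ran. The coefficients already give each dose against placebo. That limits the harm but does not make the contrasts right.

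**Conclusion.** **Pooled placebo: a cheap improvement, not an error.** The documents confirm one placebo arm across two sequential, separately randomised Parts, with no by-Part conversion analysis. They do not support saying that pooling is invalid, that drift occurred, or that any example decision would change. The sizes, about 12% against 5% for a 12-patient Part 2 dose and 8.6–14.4% against 4.6% for 3 mg/kg, hold only under the assumed 10-point shifts. The dose-selection consequence of the rise is smaller still, because closure has usually rejected the dose already.

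**Sample contrasts: wrong as written.** The reach goes beyond the supplementary analysis of the primary endpoint. Appendix I applies the code to all proportion endpoints, and logistic regression is the main model for IRAF and for sinus rhythm at 3 h, 24 h and 30 days. With three doses both contrasts are dose against dose, and in no case do the two together give each dose against placebo. The model coefficients and the primary Bayesian rule are unaffected.

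**What to change.** **SAP 8.1.** Keep the pooled posterior as primary. Add as a sensitivity analysis the reported Pr(P_d > P_0) against same-Part placebo: Part 1 placebo for 3 mg/kg, Part 2 placebo for the other doses. Tabulate placebo conversion by Part. Set no second pass/fail threshold.

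**Logistic models.** Leave the planned models for the primary and sinus-rhythm endpoints without Part. A Part term would replace the pooled analysis of the sinus-rhythm endpoints with a less precise same-Part one. A Part-adjusted fit may be shown only as a labelled sensitivity analysis, with Firth correction if one Part's placebo group has no conversions (at 10%: 0.9^18 = 15% in Part 1, 0.9^24 = 8% in Part 2). It is not worth attempting for relapse "following pharmacological cardioversion only" (SAP 8.2.2): Example 1 has 6 placebo converters, of whom 2 are in Part 1.

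**Appendix I.** Write the contrasts on `trtp` with one row per opened dose against placebo (for three doses: `1 0 0`; `0 1 0`; `0 0 1`), or output the reference-coded odds ratios directly.

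**Cost.** SAP wording and a few lines of code, with no change to design, sample size or primary rule. The same-Part result is less precise and can differ from the primary by chance. For 3 mg/kg at 56% against 14%, the chance of exceeding 0.95 is 88% with 18 controls and 95% with 42. For a 12-patient dose at an assumed 40% against 15%, it is 50% with 24 controls and 59% with 42. Nor is it fully concurrent within Part 2, where doses open and close by cohort. A concurrent-cohort figure may rest on 6 controls and should be descriptive only.

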7.1.2 Secondary Objectives

The secondary objectives of the study are as follows:

- To study the stability of rhythm control (immediate relapse of AF [IRAF], i.e. within 5 min after conversion from AF).
- To study the importance of AF duration with respect to the efficacy and safety of 1 or more dose levels of AP30663.
- To evaluate the safety and tolerability of 1 or more dose levels of AP30663.
- To study the relationship between systemic exposure and response, with special regard to the conversion from AF and the effect on QRS and QTcF.

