8 INVESTIGATIONAL PLAN

8.1 Overall Study Design and Plan: Description

This is a double-blind, randomised, placebo-controlled, parallel-group Phase 2a study of 1 or more doses of AP30663 for cardioversion in adult patients with AF. The study will be conducted in 2 parts (Part 1 and 2): Part 1 of the study is a fixed randomisation placebo-controlled parallel design, and Part 2 will be an adaptive design conducted in 1 or more further doses of AP30663 versus placebo. The study is designed to identify the dose of AP30663 to be evaluated further in later-phase research.

For both parts of the study, qualified patients will be randomised (Day 1) as soon as it is practically possible after providing their written informed consent and completion of screening procedures, but no later than 7 days after onset of the AF episode. The study drug (AP30663 or placebo) will be administered as a single intravenous infusion for 30 min on Day 1. Administration should take place as fast as possible after randomisation, and preferably no later than 12 h after randomisation. Patients may be discharged from the study site after all Day 1 procedures are completed. They will return to the study site the following day (Day 2) and for a follow-up visit on Day 30.

In Part 1 of the study, up to 36 patients will be randomised in a 1:1 ratio to receive AP30663 at 3 mg/kg or matching placebo. Their participation will last until the completion of their follow-up visit at Day 30. An interim analysis (IA) will be conducted once the randomised patients in Part 1 have completed Day 2 assessments or terminated the study. An independent data monitoring committee (DMC) will be convened to review the unblinded efficacy (including ECG and Holter ECG), PK/PD, safety and tolerability data during this IA. The recommendations of the DMC at the IA will determine the design and starting dose(s) for assessment during Part 2 of the study; the DMC may also recommend that the study to be stopped after Part 1.

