8.3.2 Inclusion Criteria

To be eligible for study entry, patients must satisfy all of the following criteria:

1. Provision of written informed consent.
2. Clinical indication for cardioversion of atrial fibrillation.
3. Current episode of symptomatic atrial fibrillation lasting between 3 h and 7 days inclusive at randomisation.
4. Adequate anticoagulation according to international and/or national guidelines.
5. Body weight 50 to 110 kg, inclusive (with clothes, without shoes).
6. Male patients and postmenopausal women aged 18 to 80 years, inclusive.
 - Male patients who are sexually active must agree to abstain from sexual activity or be willing to use a double-barrier method of birth control (i.e. any double combination of male or female condom with spermicidal gel, diaphragm, sponge or cervical cap with spermicidal gel) if they become

sexually active from the time of consent and for 90 days after the infusion day.

- Post-menopausal women are defined as being >12 months after last menstrual period.
- Women can also be included if permanently sterilised since ≥ 6 weeks (i.e. documented hysterectomy, bilateral salpingectomy, bilateral oophorectomy). Breastfeeding women are excluded.

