3.2. Secondary Objectives

The secondary objectives of the study are as follows:

- To study the stability of rhythm control (immediate relapse of AF [IRAF], *i.e.* within 5 min after conversion from AF).
- To study the importance of AF duration with respect to the efficacy and safety of one or more dose levels of AP30663.
- To evaluate the safety and tolerability of one or more dose levels of AP30663.
- To study the relationship between systemic exposure and response, with special regard to the conversion from AF and the effect on QRS and QTcF.

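### Setting a missing AF onset time to 00:00 can only lengthen recorded AF duration, by up to just under 24 h, in the variable that serves the AF-duration objective

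*SAP*

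**What the plan says.** SAP 8.1 defines the variable as "Duration of current AF episode (in hours) = date/time of randomisation – date/time of AF symptom onset" and gives one rule for incomplete data: "If no time of AF symptom onset is available, '00:00' will be used for the calculation of the duration".

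The variable is used in four places:

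- the supportive logistic regression of the primary endpoint, where "The model will include treatment and duration of current AF episode";
- the logistic models for IRAF (SAP 8.2.2) and SR (SAP 8.2.3);
- the baseline summary (SAP 7.2);
- Figure 14.2.3.15, a bar chart of conversion rate by duration, with no cut points given.

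The sample code in SAP Appendix I enters duration as one linear term with no treatment interaction. SAP 6.6 plans no subgroups.

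A secondary objective in both documents is "To study the importance of AF duration with respect to the efficacy and safety of 1 or more dose levels of AP30663" (Protocol 7.1.2; SAP 3.2). Inclusion criterion 3 requires a "Current episode of symptomatic atrial fibrillation lasting between 3 h and 7 days inclusive at randomisation".

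Protocol 11.1.7 says that missing data will not be imputed. SAP 6.3 repeats this but allows specified exceptions, and SAP section 12 lists no change from the protocol.

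**The concern.** Midnight is the earliest clock time possible on the onset date. The rule therefore does not estimate the unknown time. It picks the extreme that gives the longest episode, and the resulting errors cannot average out. Eligibility starts at 3 h, so an error of many hours can be several times the true duration of a recent episode. Patients with a recorded time carry no such error, so the rule also disturbs the ordering between timed and untimed patients.

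What is at stake is the AF-duration objective. The analyses that address it use this one variable, and the SAP plans neither a flag for imputed times nor a sensitivity analysis. At the upper end, an eligible untimed patient can be listed with a duration above seven days and so look like an eligibility deviation.

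**Working it through.** The documents give no figure that depends on AF duration, so there is none to reproduce.

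**Exact bounds (no assumptions).** Let T be true duration at randomisation and C the true onset clock time in hours after midnight. Randomisation then falls T + C hours after midnight of the onset date. The rule records T + C, so the error is C, which is at least 0 and below 24 h.

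| True duration | True onset time | Recorded | Error |
|---|---|---|---|
| 3 h | 20:00 | 3 + 20 = 23 h | +20 h |
| 3 h | 23:59 | 26.98 h | +23.98 h |
| 24 h | 18:00 | 42 h | +18 h |
| 168 h | 12:00 | 180 h | +12 h |

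**Effect on a duration slope (assumptions needed).** The documents give neither the share of missing onset times, m, nor the spread of durations. Assume that C is uniform on 0-24 h, T is uniform on (a, b), and missingness is unrelated to either.

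- Variance of T = (b − a)²/12: 36.75 for 3-24 h, 168.75 for 3-48 h, 2268.75 for 3-168 h.
- Variance of the added error = m × E(C²) − (m × E(C))² = 192m − 144m²: 17.76, 44.64 and 60 for m = 10%, 30% and 50%.
- Fraction of the slope retained = Var(T) / (Var(T) + error variance).

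| Durations | m = 10% | m = 30% | m = 50% |
|---|---|---|---|
| 3-24 h | 0.67 | 0.45 | 0.38 |
| 3-48 h | 0.91 | 0.79 | 0.74 |
| 3-168 h | 0.99 | 0.98 | 0.97 |

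The same assumptions give the share of patients with true duration of 24 h or less who are recorded above 24 h. It is m × E(T)/24 = m × 13.5/24: about 6%, 17% and 28%.

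**Effect on the treatment comparison.** A logistic simulation used 150 replicates of 2,000 patients, durations over 3-48 h, a true duration log-odds ratio of −0.02 per hour and a treatment log-odds ratio of 1.9. With 30% of times missing, the mean duration slope moved from −0.0196 to −0.0156, a ratio of 0.80 that agrees with the 0.79 above. The treatment log-odds ratio was 1.91 with none missing and 1.90 with 30% missing.

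**What a midpoint does.** The feasible onset interval on the onset date runs from 00:00 to the earlier of 24:00 and randomisation minus 3 h. Take the patient with onset at 20:00 randomised at 23:00. The interval is 00:00-20:00, its midpoint is 10:00, and the recorded duration is 13 h, an error of 10 h instead of 20 h. With the full 24 h interval the largest error is 12 h either way. With same-day onset the interval is at most 21 h, so the largest error is 10.5 h.

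For the full interval the error variance falls to m × 24²/12 = 48m. At 3-48 h and m = 30% the retained fraction becomes 168.75 / (168.75 + 14.4) = 0.92, against 0.79 under midnight.

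**The case against.** The rule is prespecified and blind to arm. It affects only patients without an onset time, a number nobody has stated. Sites must establish at least 3 h of AF, which for same-day onset needs some knowledge of the time, so missing times may be concentrated in longer episodes, where the error matters least. All of this stands. It limits the likely size of the problem but not its direction.

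It also stands that the models use all patients. With durations log-uniform over 3-168 h, infusion delays uniform over 0-12 h and 25% or 50% of times missing (all assumed), the correlation of the SAP variable with duration at infusion is already 0.986 or 0.981. Much lower correlations appear only on restriction to episodes of 24 h or less, and the SAP defines no such stratum.

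A reader might infer that early-AF patients in general are misplaced by up to a day. The documents do not support that: a patient with a recorded onset time has no midnight error.

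A reader might also infer that stopping the clock at randomisation is wrong, because conversion is timed from infusion and Protocol 8.1 says only that "Administration should take place as fast as possible after randomisation, and preferably no later than 12 h after randomisation". That is not supported as an error. The SAP uses the same clock as inclusion criterion 3, and onset to randomisation is computed correctly when the onset time is known. The size of any discrepancy depends on an assumed delay. With no missing times and durations of 24 h or less, the correlation with duration at infusion is 0.86 for delays uniform over 0-12 h and 0.995 for delays over 0-2 h. The choice of anchor is a preference.

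**Conclusion.** The point holds for patients with an onset date but no onset time. Their duration is overstated by 0 to just under 24 h, by arithmetic alone.

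The consequence is conditional. The estimated effect of AF duration can be weakened: slightly if durations spread over the whole eligible range, and substantially if most episodes are short and many times are missing. The retained fractions rest on assumed missing rates and distributions.

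The Bayesian primary analysis and the interim dose rules use only successes and patients per arm, so they are unaffected. In the simulation the treatment odds ratio did not change materially. An apparent duration above 168 h affects the Per-Protocol Set only if eligibility deviations are taken from this derived variable, which the SAP does not say. This is a cheap correction to one derivation and does not threaten the trial's main conclusion.

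**What to change.** In SAP 8.1:

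1. Replace 00:00 with the midpoint of the feasible onset interval on the onset date: 00:00 to the earlier of 24:00 and randomisation time minus 3 h.
2. Flag the imputed patients and report their number per arm.
3. Repeat the conversion, IRAF and SR logistic models with those patients excluded.
4. In SAP section 12, list the imputation as a departure from Protocol 11.1.7.
5. Keep randomisation as the main anchor. Duration to start of infusion may be added as a sensitivity covariate.

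The cost is a few lines of text and one changed derivation. No new data are needed, since infusion timing is already recorded in the eCRF (Protocol 8.4.9).

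The midpoint can err in either direction by up to about 12 h, and for some patients it does worse than midnight. With onset at 01:00 and randomisation at 23:00, the true duration is 22 h, midnight gives 23 h and the midpoint gives 13 h. The midpoint also does not remove every value above 168 h. With onset dated seven days before a 20:00 randomisation, midnight gives 168 + 20 = 188 h and the midpoint 188 − 12 = 176 h. The flag and the repeat without imputed patients cover both cases.
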